4.6.2. Benefit Assessment

COPD guidelines advocate the use of one or more long-acting bronchodilators (long-acting muscarinic receptor antagonists [LAMA]) or long-acting β 2-adrenergic receptor agonists [LABA]) in addition to inhaled corticosteroids (ICS) as second line therapy for the most advanced patients with significant symptoms and a high risk of exacerbations.

Patients enrolled in this study will receive triple combination as FF/UMEC/VI or FF/VI + UMEC. Based on available data with the components FF, UMEC and VI, it is expected that patients will potentially derive clinical benefit from studytreatment:

- Benefits of dual combination FF/VI have already been demonstrated. In clinical studies in COPD patients, FF/VI demonstrated clinically meaningful and sustained improvement in lung function and there were clinically meaningful reductions in rate of moderate or severe COPD exacerbations. FF/VI is licensed for COPD indication in a number of countries around the world.
- The UMEC/VI development program demonstrated that UMEC/VI provided clinically relevant efficacy, as defined by measures of lung function over 24 weeks of treatment, as compared with placebo, the individual monotherapies and tiotropium in a broad range of subjects with COPD. UMEC/VI is licensed for COPD indication in number of countries.
- Benefits of open triple therapy with an ICS, LAMA and LABA have been shown in published studies which assessed the use of an ‘open’ triple therapy in moderate-severe COPD patients, These studies reported improvements in lung function, HRQoL, hospitalisation rates and rescue medication use, compared to dual therapy (ICS/LABA) or LAMA alone [[Aaron, 2007](#); [Cazzola, 2007](#); [Hanania, 2012](#); [Jung, 2012](#); [Welte, 2009](#)]. These studies also showed that the number and type of reported AEs were generally similar with administration of dual or monotherapy doses for periods of up to one year, and were mostly related to their pharmacological mode of action.
- Patients with COPD have been exposed to the open triple combination FF/VI + UMEC in GSK sponsored studies. In two 12-week, placebo controlled studies (200109 and 200110), the addition of UMEC to FF/VI (100/25) once daily in adult patients with a clinical diagnosis of COPD, resulted in statistically significant and clinically meaningful improvements in the primary endpoint of trough FEV₁ at Day 85 compared to placebo plus FF/VI (124 mL (95% CI 93, 154, p<0.001) and 122 mL (95%CI 91, 152, p<0.001)). The safety profile for UMEC in combination with FF/VI was similar across treatment arms, and no additive effects or new safety concerns were identified.
- No efficacy data is available for the closed triple combination FF/UMEC/VI as the two Phase III efficacy and safety studies are currently ongoing (CTT116855, CTT116853). However, as the delivery of the components of the triple combination product (FF, UMEC and VI) are comparable when delivered as the

closed triple or the open triple, the efficacy of closed triple is expected to be as good as open triple.

The current study will provide data to demonstrate non-inferiority of closed triple and open triple on lung function. In a disease where polypharmacy is common, the 'closed' triple, once-daily combination has the potential to optimise bronchodilator therapy, improve patient adherence to therapy and, as a result, improve overall disease management in COPD patients.

4.6.3. Overall Benefit: Risk Conclusion

Current risks that have been identified for closed triple and open triple are based on the known pharmacology of the individual components FF, UMEC and VI. These include key risks of pneumonia and bone disorders/fractures from ICS-containing combinations, and the risk of adverse cardiovascular effects from LAMA/LABA-containing combinations.

The clinical development programs for dual combinations FF/VI and UMEC/VI demonstrated a favourable benefit/risk for these therapies in patients with COPD. This led to their approval and both dual combinations are now marketed for COPD indication in a number of countries around the world.

The safety profile for UMEC in combination with FF/VI was similar across treatment arms, and no additive effects or new safety concerns were identified in replicate studies in COPD patients exposed to the open triple combination FF/VI + UMEC for 12 weeks. Patients with COPD have been exposed to the closed triple combination FF/UMEC/VI as part of ongoing clinical studies (CTT116853 and CTT116855). There are currently no new safety signals based on review of blinded data from these studies. Additionally an Independent Data Monitoring Committee (IDMC) is in place for CTT116855 study, which meets periodically to review unblinded safety data.

For the current study, a safety monitoring strategy is being proposed for all the risks, including key risks (Section 4.6).

Given the clinical experience with FF, UMEC and VI, and that the associated risks with these compounds are anticipated from their known pharmacology, the potential benefit of a new therapy option in patients with moderate to severe COPD supports the conduct of this study as part of the clinical development program for closed triple combination.

5. SELECTION OF STUDY POPULATION AND WITHDRAWAL CRITERIA

Specific information regarding warnings, precautions, contraindications, adverse events, and other pertinent information on the GSK investigational product or other study treatment that may impact subject eligibility is provided in the IB.

Deviations from inclusion and exclusion criteria are not allowed because they can potentially jeopardize the scientific integrity of the study, regulatory acceptability or subject safety. Therefore, adherence to the criteria as specified in the protocol is essential.

5.1. Inclusion Criteria

Subjects eligible for enrolment in the study must meet all of the following criteria:

1. **Informed Consent:** A signed and dated written informed consent prior to study participation.
2. **Type of subject:** Outpatient.
3. **Age:** Subjects 40 years of age or older at Screening (V1).
4. **Gender:** Male or female subjects.

Females:

A female subject is eligible to participate if she is not pregnant (as confirmed by a negative urine human chorionic gonadotrophin (hCG) test), not lactating, and at least one of the following conditions applies:

- a. Non-reproductive potential defined as:
 - Pre-menopausal females with one of the following:
 - Documented tubal ligation
 - Documented hysteroscopic tubal occlusion procedure with follow-up confirmation of bilateral tubal occlusion
 - Hysterectomy
 - Documented Bilateral Oophorectomy
 - Postmenopausal defined as 12 months of spontaneous amenorrhea [in questionable cases a blood sample with simultaneous follicle stimulating hormone (FSH) and estradiol levels consistent with menopause (refer to laboratory reference ranges for confirmatory levels)]. Females on hormone replacement therapy (HRT) and whose menopausal status is in doubt will be required to use one of the highly effective contraception methods if they wish to continue their HRT during the study. Otherwise, they must discontinue HRT to allow confirmation of post-menopausal status prior to study enrolment.

- b. Reproductive potential and agrees to follow one of the options listed in the Modified List of Highly Effective Methods for Avoiding Pregnancy in Females of Reproductive Potential (FRP) (see [Appendix 5](#)) from 30 days prior to the first dose of study treatment and until after the last dose of study treatment and completion of the follow-up visit.

The investigator is responsible for ensuring that subjects understand how to properly use these methods of contraception.

5. **COPD Diagnosis:** An established clinical history of COPD in accordance with the definition by the American Thoracic Society/European Respiratory Society [[Celli, 2004](#)].
6. **Smoking History:** Current or former cigarette smokers with a history of cigarette smoking of ≥ 10 pack-years at Screening (V1) [number of pack years = (number of cigarettes per day / 20) x number of years smoked (e.g., 20 cigarettes per day for 10 years, or 10 cigarettes per day for 20 years)]. Previous smokers are defined as those who have stopped smoking for at least 6 months prior to Screening (V1).

NOTES:

- Pipe and/or cigar use cannot be used to calculate pack-year history.
7. **Severity of COPD symptoms:** A score of ≥ 10 on the COPD Assessment Test (CAT) at Screening (V1).
8. **Severity of COPD Disease:** A post-albuterol/salbutamol FEV₁/FVC ratio of < 0.70 at Screening (V1).
9. **Existing COPD maintenance treatment:** Subject must be receiving daily maintenance treatment for their COPD for at least 3 months prior to Screening (V1).

NOTES:

- Subjects receiving only PRN COPD medications are not eligible.
10. **History of Exacerbations:** Subjects must demonstrate:
- a **post-bronchodilator FEV₁ $< 50\%$** predicted normal at Screening (V1) and a documented history of ≥ 1 moderate or severe COPD exacerbation in the 12 months prior to Screening

OR

a **post-bronchodilator $50\% \leq \text{FEV}_1 < 80\%$** predicted normal at Screening (V1) and a documented history of ≥ 2 moderate exacerbations or a documented history of ≥ 1 severe COPD exacerbation (hospitalised) in the 12 months prior to Screening (V1).

NOTES:

- Percent predicted will be calculated using the European Respiratory Society Global Lung Function Initiative reference equations [[Quanjer, 2012](#)].

- A documented history of a COPD exacerbation (e.g., medical record verification) is a medical record of worsening COPD symptoms that required systemic/oral corticosteroids and/or antibiotics (for a moderate exacerbation) or hospitalisation (for a severe exacerbation). Prior use of antibiotics alone does not qualify as an exacerbation history unless the use was associated with treatment of worsening symptoms of COPD, such as increased dyspnoea, sputum volume, or sputum purulence (colour). Subject verbal reports are not acceptable.
11. **French subjects:** In France, a subject will be eligible for inclusion in this study only if either affiliated to or a beneficiary of a social security category.

5.2. Exclusion Criteria

A subject will not be eligible for inclusion in this study if any of the following criteria apply:

1. **Pregnancy:** Women who are pregnant or lactating or are planning on becoming pregnant during the study.
2. **Asthma:** Subjects with a current diagnosis of asthma. (Subjects with a prior history of asthma are eligible if they have a current diagnosis of COPD, which is the primary cause of their respiratory symptoms).
3. **α 1-antitrypsin deficiency:** Subjects with α 1-antitrypsin deficiency as the underlying cause of COPD.
4. **Other respiratory disorders:** Subjects with active tuberculosis are excluded. Subjects with other respiratory disorders (e.g. **clinically significant:** bronchiectasis, sarcoidosis, lung fibrosis, pulmonary hypertension, interstitial lung diseases) are excluded if these conditions are the primary cause of their respiratory symptoms.
5. **Lung resection:** Subjects with lung volume reduction surgery (including procedures such as endobronchial valves) within the 12 months prior to Screening (V1).
6. **Risk Factors for Pneumonia:** immune suppression (e.g. advanced HIV with high viral load and low CD4 count, Lupus on immunosuppressants that would increase risk of pneumonia) or other risk factors for pneumonia (e.g. neurological disorders affecting control of the upper airway, such as Parkinson's Disease, Myasthenia Gravis).

NOTES:

- Patients at a high risk for pneumonia (e.g. very low BMI, severely malnourished or very low FEV1) will only be included at the discretion of the investigator.
7. **Pneumonia and/or moderate or severe COPD exacerbation** that has not resolved at least 14 days prior to Screening (V1) and at least 30 days following the last dose of oral/systemic corticosteroids (if applicable).
 8. **Other Respiratory tract infections** that have not resolved at least 7 days prior to Screening (V1).

9. **Abnormal Chest x-ray:** Chest x-ray (posteroanterior and later) reveals evidence of pneumonia or a clinically significant abnormality not believed to be due to the presence of COPD, or another condition that would hinder the ability to detect an infiltrate on chest x-ray (e.g. significant cardiomegaly, pleural effusion or scarring). All subjects will have a chest x-ray at Screening (V1) [or historical radiograph or CT scan obtained within 3 months prior to Screening (V1).

NOTES:

- Subjects who have experienced pneumonia and/or moderate or severe COPD exacerbation within 3 months of Screening (V1) must provide a post pneumonia/exacerbation chest x-ray or have a chest x-ray conducted at Screening (V1).
 - For sites in Germany: If a chest x-ray (or CT scan) within 3 months prior to Screening (V1) is not available, approval to conduct a diagnostic chest x-ray will need to be obtained from the Federal Office for Radiation Protection (BfS).
10. **Other diseases/abnormalities:** Subjects with historical or current evidence of clinically significant cardiovascular, neurological, psychiatric, renal, hepatic, immunological, gastrointestinal, urogenital, nervous system, musculoskeletal, skin, sensory, endocrine (including uncontrolled diabetes or thyroid disease) or haematological abnormalities that are uncontrolled. Significant is defined as any disease that, in the opinion of the investigator, would put the safety of the subject at risk through participation, or which would affect the efficacy or safety analysis if the disease/condition exacerbated during the study.
11. **Unstable liver disease:** ALT >2xULN; and bilirubin >1.5xULN (isolated bilirubin >1.5xULN is acceptable if bilirubin is fractionated and direct bilirubin <35%)

Current active liver or biliary disease (with the exception of Gilbert's syndrome or asymptomatic gallstones or otherwise stable chronic liver disease per investigator assessment).

NOTES:

- Stable chronic liver disease should generally be defined by the absence of ascites, encephalopathy, coagulopathy, hypoalbuminaemia, oesophageal or gastric varices, or persistent jaundice, or cirrhosis.
 - Chronic stable hepatitis B and C (e.g., presence of hepatitis B surface antigen (HBsAg) or positive hepatitis C antibody test result at screening or within 3 months prior to first dose of study treatment) are acceptable if subject otherwise meets entry criteria.
12. **Unstable or life threatening cardiac disease:** subjects with any of the following at Screening (V1) would be excluded:
- Myocardial infarction or unstable angina in the last 6 months
 - Unstable or life threatening cardiac arrhythmia requiring intervention in the last 3 months
 - NYHA Class IV Heart failure

13. **Abnormal and clinically significant 12-Lead ECG finding:** Investigators will be provided with ECG reviews conducted by a centralized independent cardiologist to assist in evaluation of subject eligibility. The investigator will determine the clinical significance of each abnormal ECG finding in relation to the subject's medical history and exclude subjects who would be at undue risk by participating in the trial. An abnormal and clinically significant finding that would preclude a subject from entering the trial is defined as a 12-lead tracing that is interpreted as, but not limited to, any of the following:
 - AF with rapid ventricular rate >120 BPM;
 - sustained or nonsustained VT;
 - Second degree heart block Mobitz type II and third degree heart block (unless pacemaker or defibrillator had been inserted)
14. **Contraindications:** A history of allergy or hypersensitivity to any corticosteroid, anticholinergic/muscarinic receptor antagonist, beta₂-agonist, lactose/milk protein or magnesium stearate or a medical condition such as narrow-angle glaucoma, prostatic hypertrophy or bladder neck obstruction that, in the opinion of the investigator contraindicates study participation.
15. **Cancer:** Subjects with carcinoma that has not been in complete remission for at least 3 years. Subjects who have had carcinoma *in situ* of the cervix, squamous cell carcinoma and basal cell carcinoma of the skin would not be excluded based on the 3 year waiting period if the subject has been considered cured by treatment.
16. **Oxygen therapy:** Use of long-term oxygen therapy (LTOT) described as resting oxygen therapy >3L/min (Oxygen use ≤3L/min flow is not exclusionary.)
17. **Medication prior to spirometry:** Subjects who are medically unable to withhold their albuterol/salbutamol for the 4-hour period required prior to spirometry testing at each study visit.
18. **Drug/alcohol abuse:** Subjects with a known or suspected history of alcohol or drug abuse within the last 2 years.
19. **Non-compliance:** Subjects at risk of non-compliance, or unable to comply with the study procedures. Any infirmity, disability, or geographic location that would limit compliance for scheduled visits.
20. **Questionable validity of consent:** Subjects with a history of psychiatric disease, intellectual deficiency, poor motivation or other conditions that will limit the validity of informed consent to participate in the study.
21. **Affiliation with investigator site:** Study investigators, sub-investigators, study coordinators, employees of a participating investigator or study site, or immediate family members of the aforementioned that is involved with this study.
22. **Inability to read:** In the opinion of the investigator, any subject who is unable to read and/or would not be able to complete study related materials.

23. **Medication prior to Screening:** Use of the following medications within the following time intervals prior to Screening (V1) or requirement for their use during the study:

Table 1 Prohibited medications prior to Screening (V1)

Medication	No use within the following time intervals prior to Screening
Long term continuous antibiotic therapy for ≥ 30 days	30 days
Systemic, Oral, parenteral corticosteroids	30 days (Intra-spinal and intra-articular injections are allowed)
Any other investigational drug	30 days or 5 half lives whichever is longer.

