5.5.2. Liver Chemistry Stopping Criteria

Liver chemistry stopping and increased monitoring criteria have been designed to assure subject safety and evaluate liver event etiology (in alignment with the FDA premarketing clinical liver safety guidance).

<http://www.fda.gov/downloads/Drugs/GuidanceComplianceRegulatoryInformation/Guidances/UCM174090.pdf>

[figure not shown]
³ Based on findings from any routine labs done at site

Phase III-IV Liver Chemistry Stopping and Increased Monitoring Algorithm

Liver Safety Required Actions and Follow up Assessments Section can be found in [Appendix 2, Section 12.2](#)

Phase III-IV Liver Chemistry Increased Monitoring Algorithm with Continued Therapy for ALT ≥ 3xULN but < 8xULN

Liver Safety Required Actions and Follow up Assessments Section can be found in [Appendix 2](#), Section 12.2.

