- Demography may be captured at either the Pre-screen Visit or Screening Visit (for subjects who do not have a Pre-screen Visit).
- The IRT will be used for randomisation, emergency unblinding and study treatment supply management (Please refer RAMOS NG IRT manual for more information)
- At Screening Visit 1 both pre and post-bronchodilator spirometry will be conducted. Pre-bronchodilator spirometry will be performed prior to the subject taking their morning dose of their usual COPD treatment, between 6am and 11am and after withholding rescue albuterol/salbutamol for ≥4 hours.
- At Visits 2-5 (and the Early Withdrawal Visit), pre-bronchodilator spirometry will be performed prior to taking the morning dose of study treatment, between 6am and 11am and after withholding rescue albuterol/salbutamol for ≥4 hours.

- g. Patient reported assessments should be conducted in the following order and before other study assessments: SGRQ-C, BDI/TDI.
- h. Close out eDevice for any subject who fails to randomize, withdraws early, or completes Visit 5.
- i. Physical examination may include height, weight, blood pressure, temperature, heart rate.
- j. Vital signs must be performed prior to spirometry and prior to taking morning dose of study medication.
- k. ECG to be obtained 15 - 45 minutes post-dose at treatment Visit 5 and Early Withdrawal Visit (if possible). If a subject is not dosed at Early Withdrawal, then an ECG can be taken at any time during the visit
- l. Chest X-ray (PA and lateral) is required at Screening (or historical x-ray obtained within 3 months prior to Screening) and at anytime there is a suspected pneumonia or a mod/severe exacerbation.
- m. Pulse oximetry must be performed at V2 and anytime there is a suspected pneumonia or a moderate or severe exacerbation.
- n. PK subset A: PK samples of 120 subjects at selected sites, to be obtained at two time points at Visit 4: pre-dose and in the window 5 to 15 minutes post-dose.
PK subset B: PK samples of 60 subjects at selected sites, to be obtained and Visit 4: pre-dose, 5-15min, 45-90min, 2.5-4h, 6-8h, 10-12h, 23-24h post-dose.
- o. PK subset A: PK samples of 120 subjects at selected sites, to be obtained at two time points at Visit 5: 5 to 15 minutes post-dose and 45 to 90 minutes post-dose.
- p. The genetics blood sample should be taken at V5 or at any visit after Randomisation (V2).
- q. Haematology and chemistry panels will include liver chemistry, and potassium and glucose levels.

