7.4.6. Clinical Safety Laboratory Assessments

All protocol required laboratory assessments, as defined in [Table 3](#), must be conducted in accordance with the Laboratory Manual, and Protocol Time and Events Schedule. Laboratory requisition forms must be completed and samples must be clearly labelled with the subject number, protocol number, site/centre number, and visit date. Details for the preparation and shipment of samples will be provided by the laboratory and are detailed in the laboratory manual. Reference ranges for all safety parameters will be provided to the site by the laboratory responsible for the assessments.

If additional non-protocol specified laboratory assessments are performed at the institution's local laboratory and result in a change in subject management or are considered clinically significant by the investigator (e.g., SAE or AE or dose modification) the results must be recorded in the eCRF.

Refer to the SPM for appropriate processing and handling of samples to avoid duplicate and/or additional blood draws.

Haematology, clinical chemistry, urinalysis and additional parameters to be tested are listed in [Table 3](#).

Table 3 Protocol Required Safety Laboratory Assessments

CHEMISTRY	HEMATOLOGY	OTHER
Albumin	Haemoglobin	Hepatitis B surface antigen ¹
Alkaline phosphatase	Hematocrit	Hepatitis C virus antibody ¹
Alanine amino-transferase (ALAT or SGPT)	Platelet count	Urine pregnancy test ²
Aspartate amino-transferase (ASAT or SGOT)	WBC count	
Bilirubin, direct	Neutrophils, absolute	
Bilirubin, indirect	Neutrophils, segs (%)	
Bilirubin, total	Neutrophils, bands (%)	
Calcium	Basophils (%)	
Chloride	Eosinophils (%)	
CO ₂ content/Bicarbonate	Eosinophils, absolute	
Creatinine	Lymphocytes (%)	
Creatine phosphokinase (CPK), total	Monocytes (%)	
Gamma glutamyl transferase (GGT)	RBC count	
Glucose		
Phosphorus		
Potassium		
Protein, total serum		
Sodium		
Urea nitrogen (BUN)		
Uric Acid		

1. Assessed at Visit 1 (Screening) only, result is not exclusionary
2. Only females of child-bearing potential; refer to Time and Events Table for specific visit information

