All laboratory tests with values that are considered clinically significantly abnormal during participation in the study or within 7 days after the last dose of study treatment should be repeated until the values return to normal or baseline. If such values do not return to normal within a period judged reasonable by the investigator, the etiology should be identified and the sponsor notified.

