
ALT \geq5xULN and <8xULN and bilirubin <2xULN without symptoms believed to be related to liver injury or hypersensitivity, and who can be monitored weekly for 2 weeks.
 
OR
 
ALT \geq3xULN and <5xULN and bilirubin <2xULN without symptoms believed to be related to liver injury or hypersensitivity, and who can be monitored weekly for 4 weeks.
	
 • Notify the GSK medical monitor within 24 hours of learning of the abnormality to discuss subject safety. • Subject can continue study treatment • Subject must return weekly for repeat liver chemistries (ALT, AST, alkaline phosphatase, bilirubin) until they resolve, stabilise or return to within baseline • If at any time subject meets the liver chemistry stopping criteria, proceed as described above • If ALT decreases from ALT \geq5xULN and <8xULN to \geq3xULN but <5xULN, continue to monitor liver chemistries weekly. • If, after 4 weeks of monitoring, ALT <3xULN and bilirubin <2xULN, monitor subjects twice monthly until liver chemistries normalize or return to within baseline.

References

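### Liver exclusion 11 joins its ALT and bilirubin limits with 'and', which defeats its own bilirubin exception and admits subjects with isolated raised ALT

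*Protocol*

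**What the plan says.** Criterion 11 in Protocol Section 5.2 has a laboratory part and a clinical part. The laboratory part reads "ALT >2xULN; and bilirubin >1.5xULN (isolated bilirubin >1.5xULN is acceptable if bilirubin is fractionated and direct bilirubin <35" (per cent). The clinical part excludes "Current active liver or biliary disease", but exempts otherwise stable chronic liver disease as judged by the investigator. Its notes also admit chronic stable hepatitis B and C if the other entry criteria are met. Neither the clinical part nor the notes give an ALT value.

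For scheduled testing, footnote q of the Time and Events Table (Section 7.1) says "Haematology and chemistry panels will include liver chemistry, and potassium and glucose levels". That row is marked at Screening, Visit 5 (Week 24) and Early Withdrawal only.

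On study, Section 5.5.2 has a "Liver Chemistry Increased Monitoring Algorithm with Continued Therapy for ALT ≥ 3xULN but < 8xULN". For subjects in that range Appendix 2 (Section 12.2) adds: "Subject must return weekly for repeat liver chemistries (ALT, AST, alkaline phosphatase, bilirubin) until they resolve, stabilise or return to within baseline". Section 7.4.6 asks for repeats of "All laboratory tests with values that are considered clinically significantly abnormal during participation in the study" until they return to normal or baseline.

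**The concern.** The criterion contradicts its own exception. A bracket that re-admits some subjects with isolated raised bilirubin presupposes that isolated raised bilirubin would otherwise exclude them. Under 'and' it never does.

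Two groups that the criterion appears meant to stop then pass its laboratory part: subjects with raised ALT and bilirubin at or below 1.5xULN, and subjects with isolated raised bilirubin whose direct fraction is 35% or more. Only investigator judgement is left to exclude them, through criterion 10 or the active-liver-disease part of criterion 11.

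The exact wording matters because Section 5 of the protocol allows no deviation from the eligibility criteria and about 150 centres must apply them alike. SAP Section 4.1 summarises eligibility deviations as recorded on the eCRF, so the same subject could be eligible at one site and a deviation at another. What is at stake is subject safety and consistent screening. No effect on the trough FEV1 analysis or the mPP population is claimed.

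**Working it through.** The plan gives no figure to reproduce here, so the check is one of logic, thresholds and schedule.

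**1. Truth table for the laboratory part of criterion 11**

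| ALT >2xULN | Bilirubin >1.5xULN | 'And' | 'Or' |
|---|---|---|---|
| no | no | admitted | admitted |
| no | yes | admitted, whatever the direct fraction | excluded, unless direct <35% |
| yes | no | admitted, at any ALT | excluded |
| yes | yes | excluded | excluded |

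- Under 'and', 1 of 4 cells is excluded and the exception changes 0 cells.
- Under 'or', 3 of 4 cells are excluded before the exception. The exception then re-admits part of one cell (bilirubin only, direct <35%).

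A finer grid over ALT 0 to 10xULN, bilirubin 0 to 4xULN and direct fraction 0 to 100% gives the same answer: the exception never operates under 'and' and does operate under 'or'.

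**2. On-study thresholds (Appendix 2)**

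- Stopping: ALT ≥8xULN; 5x to <8xULN persisting at least 2 weeks; 3x to <5xULN persisting at least 4 weeks; ALT ≥3xULN with bilirubin ≥2xULN, INR >1.5 or symptoms; the same 3x and 5x bands where weekly monitoring is not possible.
- Increased monitoring: ALT ≥3xULN and <8xULN with bilirubin <2xULN and no symptoms.

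Every row needs ALT of at least 3xULN. Set against step 1, isolated ALT above 2x and below 3xULN meets no numeric rule at entry (under 'and') or on treatment. Isolated ALT of 3xULN or more also passes the entry limits literally, but it meets an Appendix 2 rule when measured on treatment. The firm gap is therefore >2x to <3xULN. Under 'or' it is empty.

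**3. Time to the next scheduled test**

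Screening is at Week -2 and the next scheduled panel is at Week 24: 2 + 24 = 26 weeks nominal, 24 of them on treatment. It is shorter if the subject withdraws early or the investigator orders a repeat.

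**4. Cost of 'or'**

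- Planned screen failures (Section 4.3): 1275 − 1020 = 255.
- The documents give no rate of isolated ALT >2xULN. Assume 0.5% to 2% of those screened.
- 0.005 × 1275 = 6.4 and 0.02 × 1275 = 25.5, so about 6 to 26 more failures.
- Relative to plan: 6.4/255 = 2.5% and 25.5/255 = 10%.

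**The case against.** The best reply is that the semicolon makes the line a list. On that reading the ALT limit and the bilirubin limit are separate items, each excludes alone, and the bracket makes sense. Table 3 in Section 7.4.6 lists "Bilirubin, direct" alongside indirect and total bilirubin, so the exception could be applied as intended. This is probably what was meant, and a site that reads it so has no gap. But the written conjunction is 'and'. The opening line of Section 5.2, under which any one criterion excludes, joins the numbered criteria and does not say how limits inside one criterion combine. No other current text restates the limits with 'or'. The documents do not show that sites did read it differently, only that they could.

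Two further points stand and limit the weight:

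- The 26-week interval and the 3xULN action threshold apply to every subject, not only to those let in by this wording. The fix removes only subjects already above 2xULN at screening.
- The 6 to 26 figure is the cost of the fix, not a count of subjects harmed. It covers all isolated ALT above 2xULN, not just the 2x to 3x band.

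Other provisions also reduce the risk. The run-in exists so that screening results are back before randomisation (Section 4.4), criterion 10 lets the investigator exclude uncontrolled hepatic abnormality, and Section 7.4.6 calls for repeats of values judged clinically significant. The liver stopping criteria may be met on any routine site laboratory result (footnote to Section 5.5.1). All but the stopping criteria rest on judgement, and the stopping criteria start at 3xULN, so none supplies a number below that.

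**Conclusion.** The concern holds. As written, criterion 11 is inconsistent with its own exception, and its literal reading leaves isolated screening ALT above 2x and below 3xULN without a numeric limit at entry or on study. The next scheduled liver test is nominally 26 weeks after screening. It also admits isolated bilirubin above 1.5xULN with a direct fraction of 35% or more, which the bracket implies is not acceptable.

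The logic and thresholds come straight from the protocol and need no assumption. How many subjects are affected cannot be known from the documents, because neither the rate of isolated raised ALT nor how sites read the line is given. The wording should be corrected because it is an operative safety threshold. It has no bearing on power or the non-inferiority conclusion.

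**What to change.** Replace 'and' with 'or' in the first line of criterion 11, so that ALT above 2xULN excludes by itself and bilirubin above 1.5xULN excludes by itself. Keep the existing exception for isolated raised bilirubin with a direct fraction below 35%. Send the same wording to all sites.

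The cost is one word, a site notice, and the few extra screen failures estimated above. No extra test is needed, because fractionated bilirubin is already in the Table 3 panel.
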